**Table 2 Protocol deviation codes and analysis sets**

Category Deviation code	Text description of deviation	Data exclusion
	Subjects are excluded from PK analysis in case of these PDs:	Exclude subject from PK analysis set
	Subjects are excluded from PD analysis in case of these PDs:	Exclude subject from PD analysis set
	Subjects are excluded from PK and PD analysis in case of these PDs:	Exclude subject from PK and PD analysis sets

If updates to this table are needed, an amendment to the SAP needs to be implemented prior to DBL.

## **5 Statistical methods for Pharmacokinetic (PK) parameters**

All subjects within the PK analysis set will be included in the PK data analysis.

### **5.1 Variables**

The following pharmacokinetic parameters will be determined from the serum concentration-time data using the actual recorded sampling times and non-compartmental method(s) with Phoenix WinNonlin (Version 6.2 or higher):

- On Day 1, 168 and 308: Cmax, Tmax
- On Days 84, 168, 252, 308 and 336: Ctrough

## 5.2 Descriptive analyses

Company Confidential Information

PK parameters will be listed by treatment group, patient and dose number. Descriptive summary statistics will include mean (arithmetic and geometric), SD, and CV (arithmetic and geometric), median, minimum, maximum and 90% CI. A geometric mean will not be reported if the dataset includes zero values. An exception to this is Tmax where median, minimum and maximum will be presented.

## 6 Statistical methods for Pharmacodynamic (PD) parameters

All subjects within the PD analysis set will be included in the PD data analysis.

### 6.1 Primary objective

The primary objective of this trial is to assess the effect of bimagrumab on fat mass at Week 48 of the treatment period.

#### 6.1.1 Variables

The primary efficacy variable is the change from baseline in fat mass (kg) at Week 48 of the treatment period. No transformation of (logarithmic or otherwise) will be done for analysis.

Since the week 48 visit is the scheduled EOT visit, and since the EOT assessments are also performed in subjects who discontinue early, only EOT assessments on subjects who completed a full treatment regimen (i.e., those who did not discontinue early) will be included in the primary analysis.

#### 6.1.2 Descriptive analyses

The individual fat mass assessments will be listed by treatment group, patient and visit/time. Summary statistics will be provided for raw, change from baseline, and percentage change from baseline by treatment group and visit/time. Summary statistics will include mean (arithmetic), SD, CV, median, minimum, maximum.

Graphical methods will be employed to show group and individual summary plots over time by treatment.

#### 6.1.3 Statistical model, assumptions and hypotheses

The primary analysis will be analyzed using a longitudinal mixed effects model. This model will have change from baseline in kg fat mass as the dependent variable, treatment arm, time, and a time\*treatment interaction as fixed effects. Baseline fat mass and baseline BMI value may

be included in the model as covariates. Time will be modeled as a categorical variable. An unstructured within-subject covariance will be used.

Company Confidential Information

#### **6.1.3.1 Handling of missing values/censoring/discontinuations**

The primary analysis model described above is valid under the assumption of data missing at random. If the dropout rate is greater than 10% in any arm, other analysis methods will be used to assess the sensitivity of the results to different methods for missing data handling.

Since the week 48 visit is the scheduled EOT visit, and since the EOT assessments are also performed in subjects who discontinue early, only EOT assessments on subjects who completed a full treatment regimen (i.e., those who did not discontinue early) will be included in the primary analysis. Thus, we will only include patients in the final analysis where the EOS visit is within 8 weeks +/- 10 days from the week 48 assessment and did not discontinue early.

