8.1 Assessment schedule

After the Screening period, visits are scheduled every 4 weeks, except during the first month of the treatment period since a visit needs to be performed at Week 2 to comply with the safety monitoring for circulating amylase and lipase.

The Assessment Schedule below lists all of the assessments and indicates with an “x” the visits when they are performed. All data obtained from these assessments must be supported in the patient’s source documentation. Assessments marked with an “S” should be assessed and documented in the patient’s source documentation but no data needs to be entered into the eCRF.

Patients should be seen for all visits on the designated day as specified in the Assessment Schedule. Until randomization, the visits should be calculated relative to the calendar date of the previous visit. After randomization, visits should be calculated relative to the calendar date of the randomization visit.

Table 8-1 Assessment schedule

Epoch	Screening		Treatment and Primary Follow-Up											
Visit Name	Screening	Baseline ¹	Treatment											
Visit Numbers	1	2	101			115	102	103	104	105	106	107		
Days	-21 to -8	-7 to -1	1			14	28	56	84	112	140	168		
Time (post-dose)	-	-	Pre-dose	0min	45min ⁶	-	-	-	-	-	-	Pre-dose	0min	45min ⁶
Informed consent	X													
Company Confidential Information														
Genetic Informed Consent	X													
Inclusion / Exclusion criteria	S	S ²												
Subjects domiciled ³		S												
Study drug administration				X			X	X	X	X	X		X	
Demography	X													
Medical history/current medical conditions	X													
Concomitant therapies	X	X		X		X	X	X	X	X	X		X	
Body Height	X													
Body Weight	X	X	X				X	X	X	X	X	X		
Waist circumference	X	X										X		
Hip measurement		X										X		
Vital Signs	X	X		X			X	X	X	X	X		X	
Physical Examination	S		S									S		
ECG evaluation	X											X		
Alcohol Test and Drug Screen	S													
Hepatitis and HIV Screen	S													
Pregnancy test	X	X	X				X	X	X	X	X	X		
Fasting insulin and glucose ⁵	X								X					
HbA1c	X		X									X		
Mixed Meal Tolerance Test ⁵														
See Table 8-2 below														
Company Confidential Information														
Blood chemistry ⁵	X	X					X	X	X	X			X	

Epoch	Screening		Treatment and Primary Follow-Up											
Visit Name	Screening	Baseline ¹	Treatment											
Visit Numbers	1	2	101			115	102	103	104	105	106	107		
Days	-21 to -8	-7 to -1	1			14	28	56	84	112	140	168		

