11.4.1 Variable(s)

The primary efficacy variable is the change from baseline in fat mass (kg) at Week 48.

Since the week 48 visit is the scheduled EOT visit, and since the EOT assessments are also performed in subjects who discontinue early (see [Section 7.2](#)), only EOT assessments on subjects who completed a full treatment regimen (i.e., those who did not discontinue early) will be included in the primary analysis.

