### **4 Statistical methods: Analysis sets**

For all analysis sets, patients will be analyzed according to the study treatment(s) received.  
The safety analysis set will include all patients that received any study drug.

The PK analysis set will include all patients with at least one available valid (i.e. not flagged for exclusion) PK concentration measurement, who received any study drug and experienced no protocol deviations that impact PK data.

The PD analysis set will include all patients with available PD data, who received any study drug and experienced no protocol deviations with relevant impact on PD data.

For subjects for which the actual treatment received does not match the randomized treatment, the treatment actually received will be used for the analysis. The analysis sets and protocol deviation codes are related as follows:

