#### **6.1.3.2 Sensitivity analyses**

Other models may be used (such as pattern-mixture models) if the dropout rate is higher than expected, in order to assess sensitivity of the primary efficacy conclusions to missing data. If a treatment effect in fat mass or HbA1c materializes, then it will be investigated whether this finding is robust under an assumption of informative drop-out; that the subjects who drop out would likely not have experienced a treatment benefit.

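### SAP 6.1.3.1 turns a rule about one scan into a rule that removes whole patients, leaving a completers-only Week 48 comparison

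*SAP*

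**What the plan says.** Protocol 11.4.1 defines the primary variable as the Week 48 change in fat mass. Because early discontinuers also have an end-of-treatment (EOT) visit, it adds that "only EOT assessments on subjects who completed a full treatment regimen (i.e., those who did not discontinue early) will be included in the primary analysis". SAP 6.1.1 repeats this. The unit being excluded is a scan.

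SAP 4 defines the analysis population: "The PD analysis set will include all patients with available PD data, who received any study drug and experienced no protocol deviations" that bear on PD data. SAP 6 then states: "All subjects within the PD analysis set will be included in the PD data analysis". Neither section mentions completing treatment or attending the end-of-study (EOS) visit.

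SAP 6.1.3.1 opens with "The primary analysis model described above is valid under the assumption of data missing at random", repeats the scan rule, and concludes that "we will only include patients in the final analysis where the EOS visit is within 8 weeks +/- 10 days from the week 48" assessment and who did not stop early. The unit is now a patient.

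The same section commits to sensitivity work: "If the dropout rate is greater than 10% in any arm, other analysis methods will be used to assess the sensitivity of the results". SAP 6.1.3.2 adds: "If a treatment effect in fat mass or HbA1c materializes, then it will be investigated whether this finding is robust" to informative dropout.

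**The concern.** The patient-level sentence is presented as a consequence of the scan rule, but it does not follow from it. It has two separate effects.

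- It removes early discontinuers entirely, including scheduled on-treatment scans that nothing else in the plan questions. A likelihood-based mixed model is protected against dropout that depends on observed values only if those values are in the model.
- It makes a completer's inclusion depend on a visit that comes after the endpoint. Protocol 3.3 gives the EOS visit another purpose, namely how well the effect lasts off drug.

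The decision margin is narrow. Protocol 11.7 assumes a true effect of 6% against a cut-off of 5% and allows for up to 30% dropout, so a shift of half a point to a point in the estimate matters. The synopsis also says that the Week 24 change is estimated from the longitudinal model. If the same exclusion carries over, observed Week 24 scans from patients who stop later are lost as well.

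**Working it through.** **1. The rules side by side**

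| Source | Unit | Completion condition | EOS condition |
|---|---|---|---|
| Protocol 11.4.1, SAP 6.1.1 | EOT scan | yes | none |
| SAP 4 and 6 | patient | none | none |
| SAP 6.1.3.1, last sentence | patient | yes | 56 ± 10 days |

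Table 8-1 reads as DXA at baseline and Days 56, 168, 336 and 392, which agrees with the five scans in Protocol 3.7.4. A patient who stops after Day 168 therefore has two valid post-baseline scans, and the last rule discards both.

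**2. The EOS window**

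8 × 7 = 56 days, so the window is 46 to 66 days. A completer on schedule has 392 − 336 = 56 days. An early discontinuer has EOS four weeks after EOT (Protocol 7.2), or 28 days, and fails both conditions.

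The window tests the gap between two visits and not the date of the scan. Protocol 8.1 says: "After randomization, visits should be calculated relative to the calendar date of the randomization visit".

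- Week 48 visit 11 days late, EOS on time: 392 − 347 = 45 days. The patient is removed.
- Both visits 30 days late: 422 − 366 = 56 days. The patient is kept.

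**3. The plan's own figures**

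Inputs from Protocol 11.7: effect 6%, SD 6.5%, 24 completers per arm, one-sided 10%, cut-off 5%.

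- SE = 6.5 × √(2/24) = 1.876.
- The significance threshold is 1.282 × 1.876 = 2.40, so the 5% cut-off is the one that binds.
- Power = Φ((6 − 5)/1.876) = 0.703, against about 70% stated.
- 68 × 0.7 = 47.6 completers, against 48 stated.

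At 30% dropout the patient-level rule removes 68 × 0.3 ≈ 20 patients.

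**4. Illustration of bias**

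Simulation of 6,000 trials per scenario, 34 per arm, scans at Weeks 8, 24 and 48, on the percentage scale of Protocol 11.7. Only the Week 48 SD of 6.5 and the Week 48 effect of 6 come from the protocol. The rest is assumed:

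- SDs 3.5 and 5.5 at Weeks 8 and 24, and effects 2.5 and 4.5.
- Correlations 0.8 (Weeks 8–24), 0.8 (Weeks 24–48) and 0.65 (Weeks 8–48).
- Dropout logistic in the latest observed change, half after Week 8 and half after Week 24, totalling 27.5% unless stated.

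OR is the odds ratio of dropout per SD of worse observed response. The all-scans estimate is maximum likelihood with treatment-by-time means and a common unstructured covariance. Monte Carlo error is about 0.02 for means and 0.6 points for probabilities.

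| Scenario | Completers only | All scheduled scans | Chance of estimate ≥ 5% (completers vs all) |
|---|---|---|---|
| Random dropout | 5.95 | 5.96 | |
| OR 2 in both arms, equal rates | 6.02 | 6.03 | |
| OR 2 placebo, 1.5 active | 5.6 | 6.0 | |
| OR 1.5 placebo, 2 active | 6.35 | 6.0 | |
| OR 2 placebo only | 5.1 | 6.0 | |
| OR 2 placebo only, 15% dropout | 5.5 | 6.0 | |
| Same rule on observed change in both arms, OR 2 (33% placebo, 22% active) | 5.7 | 6.0 | 64% vs 73% |
| Same rule, OR 3 (35% placebo, 20% active) | 5.3 | 6.0 | 56% vs 71% |
| True effect 4, OR 2 active only | 4.9 | 4.0 | 47% vs 28% |

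The two same-rule rows need no difference in how patients behave by arm. The active arm responds more, so fewer of its patients drop out.

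**5. Patients lost to the window alone**

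No visit window is visible in the plan, so a spread has to be assumed. If each visit date varies independently with SD s, the gap has SD √2 × s, and P(|gap − 56| > 10) is 0.018, 0.077, 0.157 and 0.312 for s = 3, 4, 5 and 7 days. Of 48 completers that is about 1, 4, 8 and 15.

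At s = 5, n falls to 24 × (1 − 0.157) = 20.2 per arm, SE = 6.5 × √(2/20.2) = 2.045, and the chance of an estimate of at least 5% is Φ(1/2.045) = 0.688, down from 0.703.

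**The case against.** **Intent.** The authors probably meant the EOS gap as a flag for genuine Week 48 scans, since it is 56 days in completers and 28 in discontinuers. The dropout sensitivity plans make most sense if dropouts are in the model. That is a fair reading of intent, but the sentence selects patients, and its no-early-stopping condition already separates the two groups without the window.

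**Redaction.** The term for the analysis to which the sentence applies is not defined in the visible text. Redacted sections may define it or add an all-data analysis. Neither would remove the visible conflict with SAP 4 and 6.

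**Week 48 data come from completers anyway.** True: under the scan rule too, observed Week 48 values come only from completers, and the sample size is built on 24 completers per arm. What is lost is the discontinuers' earlier scans.

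**The simulation favours the fix.** This stands in part. Every simulated dropout has a post-baseline scan and leaves for reasons visible in the scans, so the all-scans model recovers 6.0 by construction. DXA results are blinded to investigator and patient, so dropout could follow them only through a proxy. Variants of the scenario with OR 2 in placebo only (completers vs all scans):

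- one third of dropouts before Week 8: 5.10 vs 5.71
- dropout driven by the next, unobserved value: 4.88 vs 5.57
- both: 4.98 vs 5.45
- dropout driven by a proxy correlated 0.3 with DXA change: 5.72 vs 5.98

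The gap shrinks from 0.9 to about 0.3–0.7, but all scans stays closer to the truth in each.

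**Visit delays may carry over.** Protocol 3.1 also ties EOS to the last dose. With an assumed correlation of 0.5 between the two visit dates, window losses fall to 0.1%, 1.2%, 4.6% and 15.3% for SDs of 3, 4, 5 and 7 days.

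**Non-confirmatory trial.** True, and sensitivity work is promised. But the result is meant to guide development decisions (Protocol 1.4), and sensitivity analyses do not change the primary rule.

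**Conclusion.** The concern holds. SAP 6.1.3.1 and SAP 6 cannot both be programmed as written. The patient-level sentence has no basis in the protocol's primary-variable text and removes the data on which the section's own missing-data argument relies.

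The documents do not fix the size or direction of the bias. It is nil when dropout is random or has the same mechanism and rate in both arms. Under the assumed models in which response-related dropout differs, the estimate moves by roughly 0.3 to 0.9 points, in either direction, around a one-point margin. At a true effect of 4%, the chance of clearing the 5% cut-off can rise from 28% to 47%. Loss of power is a minor matter: about one percentage point even if the window removes 16% of completers at random. The Week 24 consequence depends on whether the same exclusion is applied there. This should be corrected before database lock.

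**What to change.** Delete the final sentence of SAP 6.1.3.1 and state in its place:

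- All PD-set subjects with a baseline and at least one post-baseline DXA contribute their scheduled on-treatment scans (Days 56, 168 and 336) to the mixed model.
- An early discontinuer's EOT scan is not used as a Week 48 value, as Protocol 11.4.1 and SAP 6.1.1 already require.
- Inclusion does not depend on the EOS visit.

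If a timing check is wanted, define it before database lock on the scan's own day relative to Day 336, and let it drop that scan only. Report the completers-only result as supportive.

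Using discontinuers' EOT scans at an earlier visit is a separate question. It would require Protocol 11.4.1 and SAP 6.1.1 to be amended and is not part of this change.

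The cost is a short SAP edit and minor programming. No protocol amendment, extra data or extra patients are needed.

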#### **6.1.3.2 Sensitivity analyses**

Other models may be used (such as pattern-mixture models) if the dropout rate is higher than expected, in order to assess sensitivity of the primary efficacy conclusions to missing data. If a treatment effect in fat mass or HbA1c materializes, then it will be investigated whether this finding is robust under an assumption of informative drop-out; that the subjects who drop out would likely not have experienced a treatment benefit.

#### **6.1.3.3 Supportive analyses**

Company Confidential Information

## 6.2 Secondary objectives

### 6.2.1 Variables

The secondary variables are the:

1. Body fat mass: change from baseline in fat mass after 6 months of treatment at Week 24
2. HbA1c: change from baseline will be used for inferential analysis at Week 24 and Week 48. Baseline for HbA1c is defined at the Day 1 assessment.
3. Fasting insulin and glucose at Week 12, Week 36, and EOS: Baseline for these parameters is defined at the Screening assessment.
4. HOMA2-IR: homeostatic assessment model of insulin resistance at Week 12, Week 36, and EOS
5. QUICKI: quantitative insulin sensitivity check, under fasting conditions at Week 12, Week 36, and EOS. QUICKI index will be derived from glucose and insulin levels at study completion using the following formula:

$$\text{QUICKI} = \frac{1}{\{\log(\text{Fasting Insulin}) + \log(\text{Fasting Glucose})\}}$$

6. Matsuda Index based on MTT at Week 24 and Week 48. Matsuda Index will be derived from glucose and insulin levels using the following formula:

$$\frac{10000}{\sqrt{(\text{Fasting Glucose} \times \text{Fasting Insulin}) \times (\text{Mean Glucose} \times \text{Mean Insulin})}}$$

7. Anthropometric body measurements: body weight, BMI, waist circumference, waist-to-hip ratio and lean body mass (LBM) as measured by DXA at Week 24 and Week 48.

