Time (post-dose)	-	-	Pre-dose	0min	45min ⁶	-	-	-	-	-	-	Pre-dose	0min	45min ⁶
Hematology	X	X										X		
Urinalysis		X										X		
25-Hydroxy Vitamin D	X											X		
Testosterone	X													
TSH	X													
FSH LH	X											X		

Company Confidential Information

Immunogenicity			X									X		
PK blood collection			X		X				X			X		X

Company Confidential Information

DXA scan		X						X				X		
----------	--	---	--	--	--	--	--	---	--	--	--	---	--	--

Company Confidential Information

Adverse events								X						
Dietary Counseling ⁸	X	X	X				X	X	X	X	X	X	X	X
3-day Food Record		S												S
24-hour recall dietary assessment ¹⁰		X	X				X	X	X	X	X	X	X	X

Study completion information														
Comments							X							

Epoch	Treatment & Primary Follow-up									
Visit Name	Treatment							Follow-Up	End Of Study	
Visit Numbers	108	109	110	111	112		113 ⁹	114	199	
Days	196	224	252	280	308		336	364	392	
Time (post-dose)	-	-	-	-	Pre-dose	0min	45min ⁶	-	-	
Urinalysis								X		X
25-Hydroxy Vitamin D								X		
Testosterone										
TSH										
FSH LH								X		X
Inflammatory markers								X		X
Immunogenicity								X		X
PK blood collection			X		X		X	X	X	X

Company Confidential Information

DXA scan								X		X
Company Confidential Information										
Adverse events								X		
Dietary Counseling ⁸	X	X	X	X		X		X		
3-day Food Record								S		
24-hour recall dietary assessment ¹⁰	X	X	X	X		X		X		

Company Confidential Information

Study completion information										X
Comments								X		

¹ Assessments expected at Baseline can be done on separate days between Day -7 and Day -1

² Criteria that have to be re-checked at baseline (refer to [Section 4.2](#))

³ Optional to be domiciled prior to day 1 to facilitate DXA

⁴ Company Confidential Information

⁵ Assessments need to be performed after a fast of approximately 12 hours

⁶ Time point should be calculated based on the start of the infusion

⁷ Company Confidential Information

⁸ Assessment to be conducted in-person

⁹ In the event of subject early discontinuation, visit assessments to be performed for the End of Treatment (EoT) visit

¹⁰ See [Table 8-3](#) for schedule of 24-hour recall dietary assessments performed in between monthly site visits

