#### 1.3.2. Secondary objective(s)

Secondary objective(s)	Endpoints related to secondary objective(s)

 
To evaluate the treatment effect of bimagrumab on total body fat mass after 6 months of treatment
 
	
 
Body fat mass by DXA at Week 24
 

 
To evaluate the treatment effect of bimagrumab on glycemic control and parameters of insulin sensitivity
 
	
 
HbA1c, fasting glucose and insulin, HOMA2-IR, QUICKI, Matsuda index based on MTT at Week 24 and Week 48
 

 
To evaluate the safety and tolerability of bimagrumab in overweight/obese patients with type 2 diabetes.
 
	
 
Adverse events, Vital Signs, ECG, Laboratory Values, Immunogenicity
 

 
To evaluate the pharmacokinetics of repeat doses of bimagrumab in overweight/obese patients with type 2 diabetes.
 
	
 
PK samples – pre (Ctrough) and post dose during treatment and follow-up periods. Tmax and Cmax (Day 1, Day 168 and Day 308) will be derived.
 

 
To evaluate the immunogenic response to repeat dosing of bimagrumab in overweight and obese patients with type 2 diabetes.
 
	
 
Anti-bimagrumab antibodies pre-dose, during treatment and at the end of study.
 

---

• To evaluate the treatment effect of bimagrumab on anthropometric body measurements and on lean body mass

	

• Body weight, BMI, waist circumference, waist-to-hip ratio, lean body mass (LBM) by DXA at Week 24 and at Week 48

--	--

---

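### Fasting glucose, fasting insulin, HOMA2-IR and QUICKI are endpoints at Weeks 24 and 48, but SAP 6.2.1 defines them only at Week 12, Week 36 and EOS

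*SAP*

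**What the plan says.** SAP 1.3.2 gives a single endpoint line for glycemic control and insulin sensitivity: "HbA1c, fasting glucose and insulin, HOMA2-IR, QUICKI, Matsuda index based on MTT at Week 24 and Week 48". Protocol 2.2 carries the same line.

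SAP 6.2.1, which defines the secondary variables for analysis, splits that list in two:

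- HbA1c (item 2) stays at the stated weeks: "change from baseline will be used for inferential analysis at Week 24 and Week 48". Its baseline is Day 1.
- The Matsuda index (item 6) also stays: "Matsuda Index based on MTT at Week 24 and Week 48".
- Fasting insulin and glucose (item 3) move: "Fasting insulin and glucose at Week 12, Week 36, and EOS: Baseline for these parameters is defined at the Screening assessment".
- HOMA2-IR (item 4) moves: "HOMA2-IR: homeostatic assessment model of insulin resistance at Week 12, Week 36, and EOS". No baseline is named.
- QUICKI (item 5) moves: "quantitative insulin sensitivity check, under fasting conditions at Week 12, Week 36, and EOS". No baseline is named.

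For secondary variables other than HbA1c, SAP 6.2.3 says only that an MMRM may be used, and it names no target visit for them.

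**The concern.** For four of the six measures the SAP contradicts its own endpoint table, so giving one document precedence over the other does not settle the matter. A programmer working from SAP 6.2.1 would produce no Week 24 or Week 48 result for fasting glucose, fasting insulin, HOMA2-IR or QUICKI. The protocol synopsis gives better glycemic control through improved insulin sensitivity as part of the study's main purpose, and HOMA2-IR and QUICKI are two of the three insulin indices named for it.

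If Week 24 and Week 48 values are derived later without a written rule, the derivation would be settled after data exist. The baseline is the most open part. Item 3 uses Screening and items 4 and 5 name nothing. Protocol 3.1 starts the lifestyle intervention at screening once eligibility is confirmed, so a Screening baseline and a later one need not agree.

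**Working it through.** The check compares visit lists; no power or error-rate figure is involved.

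**Inputs.** The endpoint line is in Protocol 2.2 and SAP 1.3.2, and the variable definitions are in SAP 6.2.1. Visit days come from Protocol Table 8-1, and the last-dose, follow-up and wash-out timing from Protocol 3.1 and 3.3 and Table 8-1.

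**Day to week (day / 7).** 84/7 = 12; 168/7 = 24; 252/7 = 36; 336/7 = 48; 392/7 = 56 (EOS). The last dose is at Day 308, and 308/7 = 44.

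| Measure | Endpoint line (weeks) | SAP 6.2.1 (weeks) | In common |
|---|---|---|---|
| HbA1c | 24, 48 | 24, 48 | 2 of 2 |
| Matsuda index | 24, 48 | 24, 48 | 2 of 2 |
| Fasting glucose | 24, 48 | 12, 36, 56 | 0 of 2 |
| Fasting insulin | 24, 48 | 12, 36, 56 | 0 of 2 |
| HOMA2-IR | 24, 48 | 12, 36, 56 | 0 of 2 |
| QUICKI | 24, 48 | 12, 36, 56 | 0 of 2 |

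The line promises 6 x 2 = 12 results, and 4 x 2 = 8 of them have no visit in SAP 6.2.1.

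**Distances.**

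- Week 24 to the nearest listed visits: 168 - 84 = 84 days and 252 - 168 = 84 days.
- Week 48 to EOS: 392 - 336 = 56 days.
- Last on-treatment value to end of treatment: 336 - 252 = 84 days.
- Last dose to EOS: 392 - 308 = 84 days, or 12 weeks. Protocol 3.3 puts the wash-out at about 8 weeks, so EOS is an off-drug visit.

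Gaps of 56 and 84 days are too large for visit windowing to close.

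**Which text follows the schedule?** In the readable half of Table 8-1 (Screening to Day 168), the row "Fasting insulin and glucose" is marked at Screening and Day 84 and is blank at Day 168. The HbA1c row is marked at Screening, Day 1 and Day 168. Items 3 to 5 therefore appear to follow the sampling schedule, and the conflict appears to start inside the protocol, between sections 2.2 and 8.1.

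**Could Week 24 and Week 48 values exist?** Probably, from the meal test. The same footnote applies to it and to the stand-alone sample: "Assessments need to be performed after a fast of approximately 12 hours". The Matsuda formula in item 6 takes fasting glucose and fasting insulin as inputs at those weeks. The blood chemistry panel in Protocol 8.6.6 lists no glucose, so the meal test is the only visible source.

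**The case against.** **The weeks may belong only to the Matsuda index.** Item 6 repeats the closing words of the endpoint line as a statement about Matsuda alone, so SAP 6.2.1 could be refining a loose summary. But HbA1c opens the same line, is not a meal-test measure, and is analysed by item 2 at exactly those weeks. On this reading the line would also give the four measures no timing. The reading is possible but weak.

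**The quantities are not truly undefined.** The QUICKI formula does not depend on visit, the Matsuda formula already requires fasting values at Weeks 24 and 48, and Protocol 8.5.1.3 says meal-test results will serve other insulin sensitivity parameters as well. This stands in part: a route to the values is visible. What is missing is any text that applies it to items 3 to 5. SAP 6.2.2 summarises by visit, but it summarises the variables as SAP 6.2.1 defines them.

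**With one visible source there is little to choose afterwards.** This is fair for the source sample. It does not settle the baseline, nor whether these results are to be produced at all.

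**Part of the text is not available.** Protocol 11.5 and 11.5.1, SAP section 2 and part of SAP 6.2.3 are blacked out and could contain a further rule. Table 8-2 and the later-visit fasting row of Table 8-1 are not in the text reviewed. This limits what can be said about data collection. It does not remove the contradiction, which lies wholly in visible text.

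**The impact is modest.** This stands. The study is non-confirmatory, no visible decision criterion uses these four measures, and HbA1c and Matsuda still cover Weeks 24 and 48.

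**Conclusion.** The concern holds. For four of six listed secondary measures, the visit lists in SAP 1.3.2 and SAP 6.2.1 do not overlap, and Protocol 2.2 agrees with SAP 1.3.2. As written, the visible SAP gives no result at either endpoint week and no end-of-treatment value for these measures.

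The conclusion assumes that the stated weeks govern the whole endpoint line, as the treatment of HbA1c indicates, and that no blacked-out section supplies a rule. It does not claim that Week 24 or Week 48 data go uncollected, and it does not establish which text is the wrong one. The sponsor should resolve it before database lock. The primary analysis and its power are untouched.

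**What to change.** Before database lock, reconcile Protocol 2.2, SAP 1.3.2 and SAP 6.2.1 so that all three name the same visits.

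- **Preferred.** Add Weeks 24 and 48 to SAP 6.2.1 items 3 to 5, using the fasting glucose and insulin that the Matsuda derivation needs at those visits. This assumes that Table 8-2 includes a fasting pre-meal sample, which could not be checked. For each of the four measures, name the source sample and the baseline. Keep Weeks 12 and 36 and EOS as additional visits, and label EOS as off-drug.
- **If those samples cannot be used.** Correct the endpoint line in Protocol 2.2 and SAP 1.3.2 to the visits actually sampled.

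The preferred route costs SAP wording and derivation programming. Under Protocol 8.5.1.1 the sites calculate HOMA2-IR and enter it in the CRF, so it also needs CRF entry at two more visits or a central derivation. No extra blood draw is needed if the meal test includes a fasting sample. The alternative is a one-line correction in each document.
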